### **Inclusion of Subjects Under 18 years of Age and Pregnant and Breastfeeding Women**

Adolescent subjects (12 to  $<18$  years) enrollment was initiated in this study because this population is vulnerable to infection with SARS-CoV-2 in the household ([Lewis, 2020](#)), and REGN10933+REGN10987 appears well tolerated in adults, with over 1000 adult subjects having already received REGN10933+REGN10987, either in the treatment studies (single dose of 2400 mg intravenous (IV) or 8000 mg IV [R10933-10987-COV-2066, R10933-10987-COV-2067]), or the prophylaxis study (1200 mg subcutaneous (SC) as a single dose [R10933-10987-COV-2069]), or the healthy subject safety study (1200 mg SC as multiple doses every 4 weeks (Q4W) for 6 doses [R10933-10987-COV-2093]). Upon review of safety data from approximately the first 20 adolescent subjects ( $\geq 12$  to  $<18$  years of age) enrolled, pediatric subjects aged birth to  $<12$  years of age will also be enrolled. The pediatric subjects will be analyzed as separate cohorts (cohort A1 and cohort B1) to assess the safety, PK, immunogenicity, and efficacy of REGN10933+REGN10987.

Pregnant women and breastfeeding women are being included in this study because pregnant women are at increased risk of developing severe COVID-19 ([Ellington, 2020](#)) ([Knight, 2020](#)) ([Woodworth, 2020](#)). The risks of REGN10933+REGN10987 treatment for pregnancy and a developing fetus are unknown. Because REGN10933+REGN10987 mAbs are directed against an exogenous antigen, administration of REGN10933+REGN10987 is not anticipated to affect endogenous pathways. Addition of pregnant women to the study is also supported by the results of nonclinical studies that show no changes to reproductive organs in nonhuman primates and an absence of human tissue cross reactivity with REGN10933 or REGN10987 in human or monkey tissues evaluated (see the IB). Because pregnant women are allowed in the study, contraception for women of childbearing potential (WOCBP) is no longer required as an exclusion criterion; however, all WOCBP will undergo pregnancy testing prior to dosing and at the end of study. Women who are pregnant or who become pregnant during the study will be followed for the outcome of their pregnancy. Also, because pregnant women are allowed in the study, contraception for men is no longer required as an exclusion criterion. We will not solicit information regarding pregnancies occurring in the female partners of male study subjects as the

risk of exposure is negligible in this scenario. The safety profile in pediatric subjects <12 years and pregnant and breastfeeding women is expected to be similar to that observed in adults and adolescents. Safety data is reviewed in a continuous manner by the sponsor (blinded data) and by the Data and Safety Monitoring Board (DSMB) (unblinded data).

The study has a 28-day efficacy assessment period (EAP) after the single dose of active study drug or placebo administered SC to capture all infections as detected by SARS-CoV-2 RT-qPCR positivity (both asymptomatic and symptomatic), symptomatic infection (ie, those individuals that experience symptoms consistent with SARS-CoV-2 infection and progression of COVID-19 disease). A 28-day assessment period is expected to be sufficient to accrue an adequate number of primary endpoint events within the planned sample size. The incubation period of SARS-CoV-2 after exposure is approximately 2 to 14 days (Li, 2020a) (Lauer, 2020). The duration of mild to moderate symptoms, including time to hospitalization, is approximately  $11.5 \pm 5.7$  days (Lechien, 2020). Following the 28-day EAP, subjects will undergo a 7-month follow-up period to assess for TEAEs, PK, and anti-drug antibodies (ADA) and neutralizing antibodies (NAbs). This duration is based on a half-life of 21-days for a typical mAb. This follow-up period is expected to allow an assessment of safety after discontinuing treatment. The length of the follow-up period may be modified based on the observed PK and ongoing nonclinical data as it becomes available. The occurrence and severity of any suspected COVID-19 related AEs (including SAEs) that occur as drug concentrations wane will be monitored, and subjects who received active drug or placebo will be assessed for any signal of ADE.

### 3.2.2. Subject Population

The study population will consist of approximately 3500 adult and adolescent subjects and approximately 250 pediatric subjects <12 years old, with household contact exposure to individual with a confirmed SARS-CoV-2 infection. In this study, the household contact must share the same residence and have a close exposure to the first individual in the household with a known SARS-CoV-2 infection (index case). In the case where more than 1 index case is the first known SARS-CoV-2 infected individual in the household (eg, 2 people are tested at the same time), this is allowed, and 1 index case should be chosen, at the discretion of the investigator, to be labeled “index case” in the household CRF. The study was originally planned to enroll 2000 adult and adolescent subjects. However, a blinded analysis of approximately 25% of enrolled subjects in this study was performed, demonstrating that higher than expected seropositivity was observed in cohort A. Therefore amendment 4 for the protocol increased the sample size for the study to account for the higher than expected seropositivity in cohort A. Amendment 5 for the protocol increased the sample size further to accommodate the administrative assessment of assumption verification and sample size estimation.

A household is defined as a group of people who live together at the same residence and share multiple living spaces (eg, living room, bedroom, kitchen, bathroom). In case there is uncertainty that the characteristics of the residence meets the definition of a ‘household’, the investigator and the Regeneron Medical Monitor should discuss prior to randomization.

To be included in the study, subjects must be randomized within 96 hours of collection of the index cases’ positive SARS-CoV-2 diagnostic test sample. Household contacts of individuals infected with SARS-CoV-2 are at a high risk for acquiring infection, with transmission rates ranging from approximately 10% to 15% in these settings (Burke, 2020) (Jing, 2020) (Li, 2020b). Therefore,

approximately 15% of subjects were expected to develop symptomatic disease in follow-up after a household contact transmission event (Li, 2020b). A minority of subjects were expected to be seropositive at baseline, as seropositivity in the general population, outside of hard-hit areas like New York City, was expected to be less than 10% (Burke, 2020). Upon blinded review of approximately the first 25% of subjects enrolled into this study, baseline seropositivity rates in cohort A subjects were approximately 3 times higher than anticipated and a minority of cohort A subjects who became infected during the 28 day efficacy assessment period were symptomatic. Subjects with positive rapid SARS-CoV-2 RT-PCR at the time of randomization, who are either seronegative or seropositive at baseline will also be included in the study, but only subjects who are both seronegative and negative for SARS-CoV-2 infection by central lab RT-qPCR at baseline will be included in the primary efficacy analysis.

### 3.2.3. Enrollment by Baseline SARS-CoV-2 Infection

This study will include asymptomatic subjects regardless of baseline SARS-CoV-2 infection status or serologic status. Including all-comers into the study will provide important information on infection prevention through prophylaxis as well as the impact of pre-emptive therapy in infected but asymptomatic individuals. Since the primary efficacy objective in cohort A is focused on the prevention of symptomatic SARS-CoV-2 infection (broad-term), the primary population of interest are subjects that are seronegative and SARS-CoV-2 RT-PCR negative at baseline. It was estimated that approximately 10% of the study population for cohort A would be seropositive at baseline. However, blinded data review of approximately the first 25% of subjects enrolled shows that approximately 30% of subjects in cohort A are seropositive at baseline. Therefore, the majority of subjects enrolled are expected to be allocated to the primary study population of interest, seronegative and SARS-CoV-2 RT-PCR negative at baseline (ie, cohort A).

On day 1 and prior to randomization, subjects will have a local diagnostic assay for SARS-CoV-2 from an appropriate sample. Samples will also be collected for central lab SARS-CoV-2 RT-qPCR and serology tests. The results of the local lab tests will be available the same day and will be used as stratification for randomization to allow administration of study drug. In the event that local testing results are not anticipated to be available in the time required during screening, subjects may be randomized.

For data analysis, adult and adolescent subjects will be divided into 2 independent study cohorts: cohort A or cohort B. This allocation will be based on a central lab SARS-CoV-2 RT-qPCR test result performed during the screening/baseline visit. While stratification and randomization will be based on local test results, data analyses will be based on the central lab results of baseline SARS-CoV-2 RT-qPCR results from NP swab sample and the serological status.

The analysis of the adult and adolescent subject populations that are not part of the primary study population of interest (ie, those subjects in cohort A who are seropositive at baseline) will not contribute to a primary study objective or endpoint. These individuals will be analyzed separately either through secondary or exploratory objectives and endpoints.

Adult and adolescent subjects in cohort B (ie, asymptomatic subjects who are SARS-CoV-2 RT-qPCR positive at baseline, irrespective of the serology status being positive or negative) will be analyzed separately from cohort A with a primary study objective and endpoint, secondary and exploratory objectives and endpoints. The primary efficacy objective in cohort B is focused on the prevention of COVID-19 symptoms (broad-term) in the subjects who are seronegative but

SARS-CoV-2 RT-qPCR positive at baseline. The analysis of the adult and adolescent subject populations that are not part of the primary study population of interest (ie, those subjects in cohort B who are seropositive at baseline) will not contribute to a primary study objective or endpoint. These individuals will be analyzed separately either through secondary or exploratory objectives and endpoints.

Pediatric subjects (<12 years) will be divided into 2 independent study cohorts, cohort A1 or cohort B1. This allocation will be based on a central lab SARS-CoV-2 RT-qPCR test result performed during the screening/baseline visit.

To mitigate enrollment of a high percentage of subjects that are either seropositive or SARS-CoV-2 RT-qPCR positive at baseline, those with a known prior history of a positive SARS-CoV-2 RT PCR test, a positive serology test, or COVID-19 will be excluded.

All subjects' SARS-CoV-2 qualitative diagnostic and RT-qPCR test results will be unblinded during the study. This will ensure SARS-CoV-2 infected individuals take the appropriate precautions necessary to prevent spread of disease. However, all subjects' SARS-CoV-2 serology results will remain blinded to study site personnel during the study to avoid potential bias introduced when evaluating and assessing subjects who are seropositive and to avoid encouraging higher risk behaviors through disclosure of seropositivity.

### 3.2.4. Sentinel Safety Group and Subsequent Safety Reviews

Driven by the medical urgency of the COVID-19 pandemic, the process described below is designed to maximize efficient enrollment of eligible subjects while optimizing the safety of the first SC administration of REGN10933+REGN10987. Clinical safety and tolerability data from the pooled sentinel cohorts from treatment studies (R10933-10987-COV-2066 and R10933-10987-COV-2067) in COVID-19 patients receiving IV administration of REGN10933+REGN10987 were available prior to first SC dosing in this study.

A safety review of data from an adult sentinel safety group was conducted by the unblinded IDMC/DSMB as a precondition for further enrollment across the REGN10933+REGN10987 clinical development program. The sentinel group consisted of 30 subjects pooled across the 2 treatment studies of REGN10933+REGN10987 administered as a single IV dose in patients with COVID-19 (R10933-10987-COV-2066 and R10933-10987-COV-2067). Patients in this sentinel group were randomized to receive a single IV dose of REGN10933+REGN10987 (at 1200 mg per mAb, at 4000 mg per mAb), or placebo. The IDMC/DSMB approved the continuation of the treatment studies and the initiation of the prophylaxis study. Additionally, a blinded Sponsor analysis of the adult treatment study data showed that REGN10933+REGN10987 was sufficiently well-tolerated to warrant continued enrollment as planned per protocol, with no hypersensitivity reactions or infusion-related reactions reported. Vital signs, and laboratory assessments did not identify any safety signals.

The description of the sentinel groups, safety monitoring of sentinel subjects (adult and pediatric [<12 years]), and data review for this study is provided in Section 6.1.1 and Section 6.1.2.

A blinded Sponsor analysis of the sentinel data for adult subjects in this study (R10933-10987-COV-2069) showed that REGN10933+REGN10987 was well-tolerated, with no hypersensitivity reactions or injection site reactions reported. The continuous review of blinded

safety data for the study, eg, AEs, vital signs, and laboratory assessments, have not identified any safety signals.

### 3.2.5. Primary Objective

The primary objectives of this study are:

- Cohort A: To evaluate the efficacy of REGN10933+REGN10987 compared to placebo in preventing symptomatic SARS-CoV-2 infection (broad-term) confirmed by RT-qPCR in asymptomatic subjects at risk who are seronegative at baseline.
- Cohort B: To evaluate the efficacy of REGN10933+REGN10987 compared to placebo in preventing COVID-19 symptoms (broad-term) in asymptomatic subjects that are SARS-CoV-2 RT-qPCR positive and seronegative at baseline.

The FDA Guidance on COVID-19 recommends that in prevention trials, the primary endpoint should be the occurrence of laboratory-confirmed SARS-CoV-2 infection, with or without symptoms. A descriptive administrative analysis of seronegative subjects in cohort A (n=409) demonstrated a 100% reduction in broad-term symptomatic PCR-positive infection with 8/223 (3.6%) placebo treated subjects developing symptomatic infection versus 0/186 (0%) REGN10933+REGN10987 treated subjects; OR 0.00 (0.00, 0.69) p<0.01. The revised primary objectives and endpoints for cohort A are informed by these results. Thus, these revisions are applied to objectives and endpoints for cohort B as well. The final primary objectives and endpoints for the completed study will be assessed in the final study population enrolled, excluding those that were already unblinded and assessed in the descriptive administrative analysis (Section 11.4.9). Protocol amendment 6 specifies a single primary objective and endpoint for each cohort which consists of the prevention of laboratory confirmed symptomatic SARS-CoV-2 infection (broad term)(Section 2.1.1.1 and Section 4.1.1).

**Clinical efficacy:** The ability of REGN10933+REGN10987 administration to prevent symptomatic SARS-CoV-2 infection (broad-term) will be evaluated through weekly inquiry by the investigator to assess if subjects experienced or are experiencing commonly reported clinical signs/symptoms related to COVID-19. A broad definition of signs/symptoms associated with COVID-19 (see Section 9.2.2.2 for full definition) will be utilized for the primary endpoint. Commonly reported symptoms of COVID-19 include fever, cough and myalgias. However, SARS-CoV-2 infection has been associated with a wide variety of symptoms (eg, loss of taste and smell). In order to ensure all symptomatic SARS-CoV-2 infections are captured during the study, a broad term definition of any one of 23 symptoms will be reported by the investigator in association with a laboratory confirmed SARS-CoV-2 infection (see Section 9.2.2.2).

### 3.2.6. Secondary Objectives

The secondary objectives and endpoints are informed by results of the descriptive administrative analysis and include the assessment of laboratory confirmed SARS-CoV-2 infection with or without symptoms (strict term and CDC definition as described below), the magnitude and duration of laboratory confirmed infection, and the impact of treating a COVID-19 infected household member with REGN10933+REGN10987 on the incidence of SARS-CoV-2 infection.

**Clinical efficacy:** While the primary objective captures symptomatic infections defined by a broad-term, secondary objectives include both a more strict definition of signs/symptoms

associated with COVID-19 and the CDC definition (see Section 9.2.2.2 for full definitions). Other secondary objectives will assess important clinical outcome measures including healthcare utilization (seeking an emergency room or urgent care facility, hospitalization, length of hospital stay, etc), the duration of disease in subjects who develop symptomatic infection, and the impact of index case treatment with REGN10933+REGN10987 on infection events in the study subject in this study. Similar objectives will be applied to subjects who are SARS-CoV-2 RT-PCR positive and/or seropositive at baseline (CDC, 2020b).

**Virologic efficacy:** The primary mechanism of action of REGN10933+REGN10987 is blockade of the S protein RBD interaction with ACE2, leading to inhibition of SARS-CoV-2 host cell infection. The ability of REGN10933+REGN10987 treatment to prevent SARS-CoV-2 infection will be evaluated by SARS-CoV-2 RT-qPCR test results from weekly NP swab samples. Weekly sample collection is considered an adequate collection frequency to ensure early detection of viral load (SARS-CoV-2 RT-qPCR positivity) in infected individuals; this is based on the average duration of viral positivity from NP swabs that ranges from 7 to 28 days (He, 2020) (Wölfel, 2020). All subjects will have SARS-CoV-2 RT-qPCR testing by NP sample. Nasopharyngeal swab testing has been shown to have good sensitivity and specificity for detecting SARS-CoV-2 RNA (Zou, 2020) (Pere, 2020). The administrative assessment of seronegative subjects (n=409) in cohort A demonstrated that the risk of becoming infected (ie, becoming SARS-CoV-2 RT-PCR positive) was reduced as early as the first week of study (10.3% in subjects in the placebo group versus 5.4% in subjects in the REGN10933+REGN10987 group at day 8). The protection continued through the following weeks. Both the magnitude and duration of infection were reduced by REGN10933+REGN10987 treatment. Infections occurring in subjects in the placebo group had, on average, more than 100-fold higher peak viral load. Infections in subjects in the REGN10933+REGN10987 group lasted no more than 1 week, while approximately 40% of infections in subjects in the placebo group lasted 3 to 4 weeks. No infected subjects in the REGN10933+REGN10987 group had high viral loads ( $>10^4$  copies/mL) compared to 62% of the infected subjects in the placebo group (13/21 placebo versus 0/9 REGN10933+REGN10987) (CDC, 2020b). (CDC, 2020b)

### 3.2.7. Rationale for Dose Selection

This study will assess a single SC dose of REGN10933+REGN10987 as combination therapy in a 1:1 ratio. The 1:1 ratio for REGN10933+REGN10987 is thought to be appropriate as these are noncompeting mAbs targeting non-overlapping epitopes of the RBD of the S protein of SARS-CoV-2, with similar in vitro binding and neutralization properties (for more information, refer to the IB). The study will evaluate REGN10933+REGN10987 as combination therapy at a 1200 mg (600 mg of each mAb) SC dose.

Angiotensin converting enzyme subtype 2 expression has been reported in the lungs, particularly in type-2 alveolar epithelial cells and bronchial airway epithelium (Wu, 2020) (Xu, 2020) (Zhao, 2020). The strategy taken for dose selection in this study was to identify a target concentration in lung epithelial lining fluid (ELF) that approximates the effective concentration required for 99% neutralization (EC99) of SARS-CoV-2 in vitro and to then identify a dose that will meet or exceed this concentration in lung ELF. The EC99 against SARS-CoV-2 in vitro is 0.14 µg/mL for REGN10933 and 0.80 µg/mL for REGN10987.

An average lung ELF-to-serum mean  $C_{max}$  ratio of ~0.15 has been reported for other exogenous IgG1 mAbs for the treatment of *Staphylococcus aureus* lung infections ([Magyarics, 2019](#)). It is assumed that the lung ELF-to-serum  $C_{max}$  ratio is 0.15 for REGN10933 and REGN10987. Dividing the target lung ELF concentration by this ratio, the associated serum concentration for these targets is therefore estimated to be ~at least 5  $\mu$ g/mL for the combination of REGN10987+REGN10933.

Taking into account uncertainties regarding mAb penetration into lung ELF, prediction of human PK, and effects of disease on PK, 20  $\mu$ g/mL was selected as a target concentration in serum for subjects using the 600 mg SC per mAb REGN10933+REGN10987 combination dose. The goal for this REGN10933+REGN10987 combination dose is for  $\geq 95\%$  of subjects to exceed the target serum concentration for 28 days after dosing. To estimate the clinical SC dose required to achieve this goal, a population PK model developed for a typical Regeneron mAb administered SC was used to simulate mean and 5th percentile serum concentrations for a virtual population of 2000 subjects (mean (SD) [min, max] body weight of 85 (17) [40, 150] kg) for various SC doses.

For a single 600 mg per mAb SC dose,  $\geq 95\%$  of adult subjects are predicted to exceed the target serum concentration by approximately 1 day after the first dose and remain above the target serum concentration for the remainder of the 28-day treatment period, for each mAb.

As the lower end of the proposed body weight range for adolescent subjects  $\geq 12$  years of age (40 kg) falls within the range of expected body weights for adult subjects, similar exposures are expected between these 2 populations for a single 1200 mg (600 mg of each mAb) SC dose of REGN10933+REGN10987.

Similar to adults, the goal for dose selection in the pediatric population is for  $\geq 95\%$  of pediatric subjects within each weight-tiered group to exceed the 20  $\mu$ g/mL target concentration in serum per mAb for 28 days after dosing. An additional consideration was to select doses for pediatric subjects that would achieve exposures within the range of those shown to be generally safe and well tolerated in adults.

The same 2-compartment population PK model with linear clearance developed for adults was used to simulate concentrations in serum over time for various doses in each pediatric weight-tiered group using allometrically scaled estimates of clearance and volume of distribution (gestational-age corrected allometrically scaled estimates were used for subjects <10 kg) ([Robbie, 2012](#)). The doses selected are predicted to result in  $\geq 95\%$  of subjects within each weight tier exceeding the 20  $\mu$ g/mL target concentration in serum per mAb for 28 days after dosing ([Table 1](#)). Compared to predicted 95th percentiles of  $C_{max}$  and  $AUC_{0-28}$  for REGN10933 and REGN10987 in adults after a single SC dose of 1200 mg (600 mg per mAb), the 95th percentiles of predicted  $C_{max}$  and  $AUC_{0-28}$  across the different pediatric weight-tiered groups ranged from 18% to 88% higher than in adults, but lower than observed mean  $C_{max}$  and  $AUC_{0-28}$  values for the lowest single IV dose (2.4 g) with an acceptable safety profile in adults with COVID-19. For children < 10 kg, SC administration is not deemed feasible, and it is assumed that the concentration-time profile of REGN10933 and REGN10987 will be similar for intramuscular (IM) and SC administration.

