### 7.2.1. Inclusion Criteria

A subject must meet the following criteria to be eligible for inclusion in the study:

1. Adult subjects 18 years of age (irrespective of weight) and above at the signing of informed consent or adolescent subjects  $\geq 12$  to  $<18$  years of age, or pediatric subjects  $<12$  years of age at the signing of the assent (parent/guardian sign the informed consent) (see Section 13.2)
2. Asymptomatic household contact with exposure to an individual with a diagnosis of SARS-CoV-2 infection (index case). To be included in the study, subjects must be randomized within 96 hours of collection of the index cases' positive SARS-CoV-2 diagnostic test sample
3. Subject anticipates living in the same household with the index case until study day 29
4. Is judged by the investigator to be in good health based on medical history and physical examination at screening/baseline, including subjects who are healthy or have a chronic, stable medical condition
5. Willing and able to comply with study visits and study-related procedures/assessments.
6. Provide informed consent signed by study subject or legally acceptable representative.

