#### Matching placebo:

- Supplied as matching solution for SC or IM injection.

All adult or adolescent subjects will receive 4 SC injections of study drug on day 1, each injection containing 2.5 mL of active study drug or placebo. The REGN10987 and REGN10933 dose is 1200 mg (600 mg of each mAb) SC single dose on day 1.

Pediatric subjects (<12 years of age) will receive between 1 to 4 SC or IM injections of study drug, active or placebo, depending on the weight-tiered dose group on day 1 (Table 2). Subjects <5 kg should not receive an injection with more than 1 mL, subjects between 5 and 10 kg should not receive an injection with more than 1.25 mL. Subjects <10 kg may receive IM injection(s) at the discretion of the investigator, as children less than 10 kg have smaller amounts of subcutaneous tissue and IM injection may be better tolerated than SC. In addition, in children <10 kg, the combined volume containing both mAbs may be administered in a single syringe. The total volume of study drug per syringe and the number of injections will be recorded in the CRF. For subjects who weigh  $\geq 10$  kg, study drug may be administered SC using an infusion pump, containing the combined volume containing both mAbs, which may improve tolerability of administration as only 1 injection may be required.

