**Table 2: Weight-Tiered Dose Groups for Pediatric Subjects <12 Years of Age**

Weight-Tiered Dose Group	Total Dose (mg)	Route of Administration	Total Number of Injections	Total Volume (mL) of Injection
≥40 kg	1200 (600 per mAb)	SC 	4	10 (5 per mAb)
≥20 to <40 kg	792 (396 per mAb)	SC 	4	6.6 (3.3 per mAb)
≥10 to <20 kg	408 (204 per mAb)	SC 	2 or 4	3.4  (1.7 per mAb)
≥5 to <10 kg 	144 (72 per mAb)	IM	1 or 2	1.2  (0.6 per mAb)
≥2.5 to <5 kg 	96 (48 per mAb)	IM	1	0.8 (0.4 per mAb)
<2.5 kg 	48 (24 per mAb)	IM	1	0.4 (0.2 per mAb)

1. Investigators have the option to use an infusion pump for SC administration of study drug containing the combined volume with both mAbs.
2. If the Investigators prefers not to exceed 1 mL per syringe, then study drug may be administered using 2 syringes for each mAb (ie, 4 injections), one with 0.8 mL and another with 0.9 mL for each mAb. If the Investigator prefers to use only 2 syringes (ie, 2 injections), the 1.7 mL administered in each syringe will contain a different mAb.
3. Investigators have the option to administer the dose in a single syringe containing the combined volume with both mAbs.
4. If the Investigator prefers not to exceed 1 mL per syringe, then study drug may be administered using 1 syringe for each mAb. If the Investigator prefers to use 1 syringe, the 1.2 mL administered in 1 syringe should be combined volume of 0.6 mL of each mAb.

For study drug administration which requires multiple SC injections, it is recommended to use different quadrants of the abdomen (avoiding navel and waist areas) and upper thighs. During the dose administration, each injection must be given in a different anatomical location (eg, 1 injection administered in the right lower quadrant of the abdomen, another in the left lower quadrant of the abdomen, etc). For pediatric subjects (<12 years) only, a numbing cream may be used at the planned site(s) of injection. Adolescent (≥12 years) and adult subjects should not use numbing cream at the sites of injection as this will interfere with the safety assessment, ie, evaluation of injection site reactions.

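### The adolescent 1200 mg dose is justified from a 40 kg lower weight, but no eligibility or dosing rule sets a minimum weight for ages 12 to <18 years

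*Protocol*

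**What the plan says.** **Dose rationale (Protocol 3.2.7).** The adult dose was chosen by simulating a "virtual population of 2000 subjects (mean (SD) [min, max] body weight of 85 (17) [40, 150] kg) for various SC doses". Adolescents were not simulated separately. The argument for them begins "As the lower end of the proposed body weight range for adolescent subjects", puts that lower end at 40 kg, and concludes that exposure at 1200 mg should resemble that of adults.

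**Pediatric tiers (Protocol 3.2.7 and Table 2).** For younger children the work was done tier by tier: "The same 2-compartment population PK model with linear clearance developed for adults was used to simulate concentrations in serum over time for various doses". Results are given only for the doses selected. Compared with adults, the predicted 95th percentiles of Cmax and AUC over 28 days "across the different pediatric weight-tiered groups ranged from 18% to 88% higher than in adults, but lower than observed mean" exposure. The comparator is the exposure observed "for the lowest single IV dose (2.4 g) with an acceptable safety profile in adults with COVID-19". The tiers carry the title "Weight-Tiered Dose Groups for Pediatric Subjects <12 Years of Age". They assign 792 mg at 20 to <40 kg and 1200 mg from 40 kg upward.

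**Eligibility and dosing.** Criterion 1 in Protocol 7.2.1 reads "Adult subjects 18 years of age (irrespective of weight) and above at the signing of informed consent or adolescent subjects" and then gives the adolescent age band alone. Weight is mentioned only for adults, and there to say that it does not matter. Section 8.1 states "All adult or adolescent subjects will receive 4 SC injections of study drug on day 1", each of 2.5 mL.

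**The concern.** The rationale is conditional on a weight floor, and the sections that control enrollment and dosing do not contain that floor. A 12-year-old of 32 kg would be eligible and would receive 1200 mg, whereas an 11-year-old of the same weight would receive 792 mg. The plan gives no reason why the weight adjustment should stop at the twelfth birthday.

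What is at stake is the exposure justification for dosing some minors. Over-exposure cannot threaten the 20 µg/mL serum target. The randomized comparison is also unaffected, because the rule is the same in both arms.

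**Working it through.** **1. Reproduce the plan's doses.** Section 8.1 gives 120 mg/mL for each antibody.
- Adult and adolescent: 4 × 2.5 mL × 120 mg/mL = 1200 mg, as stated.
- Tier of 20 to <40 kg: 6.6 mL × 120 mg/mL = 792 mg, as stated.

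**2. Look for the 40 kg floor in current text.**
- Inclusion criterion 1 (7.2.1): none for ages 12 to <18.
- Exclusion criteria (7.2.2): none.
- Randomization strata (8.4): weight is used only below 12 years.
- Dosing (8.1): fixed for all adolescents.

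The amendment history mentions 40 kg for adolescents, but it records past changes and is not an eligibility rule. I give it no weight.

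**3. Dose ratio at equal weight.** 1200/792 = 1.515. At 30 kg, 1200 mg is 40 mg/kg and 792 mg is 26.4 mg/kg. A 40 kg subject on 1200 mg receives 30 mg/kg.

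**4. Upper view from the reported range.** With linear clearance, exposure at a given weight scales with dose. If the 792 mg tier's 95th percentile lies between 1.18 and 1.88 times adults, 1200 mg in that tier would give:
- 1.18 × 1.515 = 1.79
- 1.88 × 1.515 = 2.85

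This overstates the likely effect. The 18% to 88% range pools all tiers, including IM-dosed infants, and adolescents under 40 kg are probably near the top of the 20 to <40 kg tier. The tier's own figure is not reported.

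**5. By weight.** AUC at 1200 mg relative to a 40 kg subject is (40/W)^b. The exponent b is not in the documents; I assume 0.75 to 1.0.

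| Weight | b = 0.75 | b = 1.0 |
|---|---|---|
| 39 kg | 1.02 | 1.03 |
| 35 kg | 1.11 | 1.14 |
| 30 kg | 1.24 | 1.33 |
| 25 kg | 1.42 | 1.60 |

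**6. Against exposure the plan already accepts.** The highest typical AUC in the 792 mg tier is at 20 kg. A 1200 mg dose gives the same AUC at W = 20 × 1.515^(1/b), which is 34.8 kg (b = 0.75) or 30.3 kg (b = 1.0). Only below about 30 to 35 kg would a typical adolescent exceed it.

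**7. Simulated 95th percentiles of AUC, as ratios to adults.** Adult weights are normal 85 (17), truncated to 40 to 150 kg. AUC is (dose/1200) × (85/W)^b with lognormal error. Assumptions: between-subject CV 20% to 40%, b from 0.75 to 1.0, and uniform weights within each band.
- 792 mg, 20 to 40 kg: 1.43 to 1.85, inside the protocol's 1.18 to 1.88, so the simple model is consistent with the reported range.
- 1200 mg, 35 to 40 kg: 1.67 to 2.04.
- 1200 mg, 30 to 40 kg: 1.78 to 2.22.

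**The case against.** The strongest reply is that the effect is small and the safety margin wide. More than 1000 adults had already received the combination, in regimens that included single IV doses of 2400 mg and 8000 mg (3.2.1). Both IV doses were well tolerated in the sentinel groups. Monkeys tolerated up to 150 mg/kg per antibody weekly for four weeks, against a single 600/30 = 20 mg/kg per antibody in a 30 kg adolescent. Adolescent TEAEs are summarized (Protocol 11.4.5.1), safety is analyzed for ages 12 to <18 (SAP 5.8), and the Safety Review Committee looks at adolescents separately (6.3.2). Exclusion criterion 6 lets the investigator decline anyone at added risk. All of this stands and limits the severity. None of it supplies the missing weight rule.

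Four stronger readings are tempting, and the documents do not support them.

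- **That 1.88 is a ceiling which 1200 mg would breach.** The 18% to 88% range describes the selected doses. The stated benchmark is mean exposure at 2.4 g IV, and those values are not given, so neither compliance nor breach can be shown.
- **That the gap is peculiar to adolescents.** The adult simulation also stops at 40 kg, and adults are admitted at any weight. Under the simulated normal distribution, about 0.4% of adults would weigh less than 40 kg. The adolescent case differs in that its written argument names 40 kg as the lower limit and a lower dose for that weight already exists in the same protocol.
- **That adolescent PK is absent.** Adolescents are in subset 3, which has no scheduled PK, but a sample follows a positive RT-qPCR (6.1.4). The scheduled-PK subsets had already filled when adolescents were added (6.1).
- **That light adolescents were in fact overdosed.** The documents identify no adolescent under 40 kg.

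**Conclusion.** The mismatch is real and minor. Current text allows 1200 mg in adolescents below the weight on which that dose was justified. At 20 to <40 kg this is 1.52 times the dose for a younger child of equal weight, with no exposure result reported.

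The dose ratio comes directly from the documents. The exposure figures rest on an assumed exponent of 0.75 to 1.0, and the simulated ratios also on assumed weights and variability. On those assumptions the excess over a 40 kg subject is negligible near 40 kg and about a quarter to a third at 30 kg. The number of subjects affected is unknown and possibly small. Efficacy conclusions do not change.

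**What to change.** Either change aligns the rule with the rationale:

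- add a minimum of 40 kg for ages 12 to <18 years to inclusion criterion 1; or
- in section 8.1, apply the Table 2 dose of 792 mg at 20 to <40 kg to adolescents as well.

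The cost is one phrase or one dosing rule. The downside is that a few light adolescents are excluded or need a weight-based dose. Adults under 40 kg remain as they are, because the protocol admits them explicitly.

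Enrollment may already be over: Protocol 11.4.9 counts about 269 subjects randomized after 28 January 2021. If it has closed, report the number of treated adolescents under 40 kg and their TEAEs by treatment group. Weight is already collected, but the SAP 4.1 categories cut only at 10 and 20 kg, so no planned summary isolates this group. The cost is one small table.
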